5.1 Patient Disposition

A chart of the patients included in the study, as well as those who are not evaluable, and the reasons for this will be displayed.

6 METHODS FOR THE STATISTICAL ANALYSIS

The analysis methods to be used to achieve the study objectives and draw up the descriptive content for the variables are detailed below.

❖ UNIVARIATE ANALYSIS

Quantitative variables will be described with centralization and scattering measures (mean, SD (standard deviation), median, minimum, maximum, Q1 (first quartile), Q3 (third quartile and N).

Qualitative variables will be described by absolute and relative frequencies. Two columns of percentages will be presented: Total Percentage (Total %) and Valid Percentage (Valid %):

- Total Percentage (%): Percentage of the sum of valid responses plus missing values, i.e. of the total of the sample under study.
- Valid percentage (Valid %): Percentage of total valid responses, i.e. with data on the variable.

In subgroup analyses, only the valid % with respect to the total for each group will be presented.

For questions with more than one answer option, **multiple response** tables will be shown. Two percentage column will be shown in these tables:

- Total percentage (%) Percentage of the sum of valid responses plus missing values, i.e. of the total of the sample under study. Since it is multiple choice, the sum of percentages does not have to be 100 (the percentage may be exceeded).
- Valid percentage (%) Percentage of the number of patients with at least one given answer from among the possible answers. Since it is multiple choice, the sum of percentages does not have to be 100 (the percentage may be exceeded).

Missing data will not be attributed and will be left as lost data.

Statistical analysis of variables collected in the study will be performed using the SPSS statistical program.

NOTE 1: Due to the small number of patients available in the study, no comparisons will be made and the associated p-value will not be shown. Only descriptive analyses will be presented.

NOTE 2: The texts collected in open fields will not be grouped, other than to standardize format and spelling. If desired, any grouping must be performed by the sponsor and as an additional table to the description of what is included in the database.

6.1 Visit reassignment

6.1.1 Numerical variables at follow-up (neurological and scales)

In the section on variables in follow-up, there are visit dates and no months assigned to those visits. To avoid time variability and ensure consistency of the data, for each quantitative follow-up variable, the following procedure will be calculated. All values will be assigned, as of the follow-up date, weighing the assignments based on the recorded follow-ups.

1. Months between visits:

Firstly, the date difference between the first follow-up and the start time will be calculated for the variable in question. Values will be assigned to those visits that are close to this difference or lower, i.e. if the difference is 25 months, visits up to Month 24 will be allocated (see note 3 below).

2. Monthly unit change (exchange rate):

$$\frac{(\text{value at follow-up visit} - \text{value at start of treatment visit})}{\text{months between visits}}$$

3. Increment for each visit:

Monthly unit change x 6

Monthly unit change x 12

Monthly unit change x 18

Monthly unit change x 24

Monthly unit change x 36

4. Value assigned at each visit:

Baseline value + Increment for each visit

NOTE 3:

- In case only one follow-up is available and the total follow-ups cannot be assigned, the “last value carried forward” (LVCF) method will be used, so the last value obtained will be carried over to the end.
- If more than one follow-up is available and the difference between their dates is:
 - Less than 5 months, the value will not be allocated, as the two visits would be very close to each other.
 - Greater than 5 months and less than 10 months, the value of that follow-up will be assigned to the next follow-up pending assignment. That is, if the assignment of the first follow-up

reaches month 24, the assignment of month 36 would be considered as the value recorded in the second follow-up.

– Otherwise, if the difference is greater than 10 months, the values will be assigned with the algorithm from step 1 taking the previous follow-up as baseline.

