In a retrospective study conducted in 210 patients with ATTRv in treatment with tafamidis 20 mg and with a follow-up of 18-66 months, it was observed that patients classified as non-responders had lower drug concentrations. The outcomes of this study support the hypothesis that ATTRv patients with polyneuropathy may benefit from a higher dose of tafamidis (Monteiro C, et al)²³.

Due to the phenotypic heterogeneity of ATTR patients and the growing demand for real-world data on the effect of tafamidis 61 mg in patients with systemic involvement, our objective is to conduct a retrospective study to evaluate the efficacy of tafamidis 61 mg in non-cardiac variables in patients with ATTRv and ATTRwt, included in the ATTR-ACT (B3461028) and LTE (B3461045) in Spain. To do this, extra-cardiac clinical data will be collected throughout the follow-up and treatment period with tafamidis 61 mg, in order to evaluate the efficacy of treatment in ATTR patients with neurologic involvement.

To date, little information has been published on the demographic and clinical characteristics of clinically overt Spanish ATTR patients (González-Moreno J, et al; Silva Hérnandez, et al; Álvarez-Rubio J, et al.)⁶⁻⁸, and even less international data have been published on neurologic involvement in ATTRwt patients (González-Moreno J, et al; Kharoubi M, et al; Wajnsztajn Yungher F, et al; Russell A, et al; Papagianni A, et al; Kleefeld F, et al)^{6, 9-13}. In addition, this study will provide an overview of Spanish patients with mixed phenotype and provide real-world data on the deterioration of polyneuropathy and management of ATTRwt patients.

There is currently no published data on the use of tafamidis free acid 61 mg in patients with ATTR-PN, therefore this study addresses an unmet medical need and may yield on the efficacy of tafamidis free acid 61 mg in patients with mixed phenotype ATTRv and in ATTRwt patients with neurologic involvement.

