9.2. Setting

The current study population consists of ATTRv and ATTRwt patients who have participated in studies B3461028 and B3461045 in Spain, with cardiac and neurologic involvement receiving or have received tafamidis free acid 61 mg for at least 12 months, and who are in neurological

PFIZER CONFIDENTIAL

follow-up for no less than 12 months. To our knowledge, 17 ATTRv patients have been included in these studies.

Individuals participating in the TRAMA study must meet all of the inclusion and none of the exclusion criteria described in Section 9.2.1.

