9.3. Variables

The variables to be collected from each patient at participating sites will be:

- Clinical parameters available in their medical history in the 12 months prior to their inclusion in studies B3461028 and/or LTE (B3461045).
- Clinical parameters available in their medical history at the time of inclusion in studies B3461028 and/or LTE (B3461045) (last visit to the site before inclusion in the study).
- Routine follow-up visits (up to the last available visit prior to enrollment in the TRAMA study).

The variables to be collected from each individual's medical history during the course of this study will be:

- **Treatment-related variables:**

- Date of consent signature for entry into study B3461028 and B3461045
- ATTR Treatment Start Date:
 - Initiation of treatment with commercial medication (tafamidis 20 mg)
 - Treatment regimen in the trial of ATTR-ACT or LTE tafamidis 20 mg
 - Treatment regimen in the ATTR-ACT or LTE tafamidis 80 mg or 61 mg trial
- Patient is currently on treatment with tafamidis free acid 61 mg (if not, specify stop date)

- **Demographic variables:**

[figure not shown]
- Age, gender
- Genotype: mutations (homozygosity/heterozygosity) or wt
- Age of disease onset (in order to characterize whether the disease onset was neurological or cardiological and to understand why it was not treated with available therapeutic options)
- First disease-related sign or symptom
- Age at disease diagnosis

- **Variables collected at each follow-up visit:**

- **Extra-cardiac 'red flags' medical history:**

- Carpal tunnel syndrome (if yes, if there was a surgery/date)
 - Lumbar stenosis
 - Gastrointestinal disturbances: diarrhea/constipation, early satiety

PFIZER CONFIDENTIAL

- Urological disturbances: urinary tract infections, urinary incontinence, urinary infections, incomplete emptying sensation
- Ophthalmological disturbances
- Central nervous system (CNS) disturbances (seizures, stroke or transient ischemic attack, cognitive impairment)
- Symptoms of autonomic neuropathy: impaired sweating, sexual dysfunction, orthostatic hypotension
- Symptoms of peripheral neuropathy (allodynia, paresthesia, hyperalgesia...)
- Unintentional weight loss

- Modified Body Mass Index (mBMI)
- Neurological variables:
 - NIS (*Neuropathy Impairment Score*)
 - NIS-LL (*Neuropathy Impairment Score Lower Limbs*)
 - PND (*Polyneuropathy disability score*)
 - FAP (*Family Amyloidotic polyneuropathy stage*)
- Neurophysiological variables:

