9.5. Study size

The population of this study consists of the ATTRv and ATTRwt patients included in studies B3461028 and B3461045 in Spain, who present with multisystem involvement (cardiac and neurological), who are currently receiving or have received treatment with tafamidis free acid 61 mg for at least 12 months; and who have a neurological follow-up of at least 12 months. To our knowledge, ~~co~~ ATTRv patients have been included in studies B3461028 and B3461045 studies in

Spain. Patients who respond to the inclusion criteria are estimated to be ~~cc1~~ with ATTRv and ~~cc1~~ with ATTRwt.

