4 STUDY POPULATION

The current study population consists of ATTRv and ATTRwt patients who have participated in studies B3461028 and B3461045 in Spain, with cardiac and neurologic involvement receiving or who have received Tafamidis free acid 61 mg for at least 12 months, and who are in neurological follow-up for no less than 12 months. According to the protocol, patients who meet the inclusion criteria are estimated to be: 10 with ATTRv and 10 with ATTRwt.

Individuals participating in the TRAMA study must meet all of the inclusion and none of the exclusion criteria.

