5 POPULATION TO BE ANALYZED

The patient's classification is defined below based on compliance with the screening criteria:

- ***Evaluable patients*** are defined as those who meet all of the inclusion criteria and none of the exclusion criteria described in the protocol.
- ***Non-evaluable patients*** are defined as those who fail to meet any of the inclusion criteria or meet one or more exclusion criteria.

Information regarding the screening criteria in the form of a binary variable (Yes / No) is recorded on the CRF for each item described.

Several of these criteria can be checked against the data collected in the CRF. The criteria that will be verified in order to define the evaluable population are described below:

Inclusion Criteria

Patients must meet all of the following inclusion criteria to be eligible for this study:

1. *Be of legal age (>18 years).*

Age of all patients at enrollment will be checked to ensure they are 18 years old or above.

2. *Have participated in studies B3461028 and/or B3461045 in Spain.*

A check will be carried out to ensure patients have answered 'yes' to one of the following questions:

- Has the patient participated in study B3461028?
- Has the patient participated in study B3461045?

It will also be confirmed that they have collected the date of the consent indicated for the corresponding previous study.

3. Have been treated for at least 12 months with Tafamidis free acid 61 mg.

The difference between the Tafamidis 61 mg end date minus its start date will be checked to ensure it is at least 12 months, or otherwise the Tafamidis 80 mg end date minus its start date is at least 12 months:

(End date* - start date* \geq 12 months)

*Dates for Tafamidis 61 mg or 80 mg

In such cases where they are on treatment with Tafamidis 61 mg, the date of inclusion in this study will be considered as “End Date”.

4. Have a minimum of 12 months of neurological follow-up after starting treatment with Tafamidis free acid 61 mg and have data from previous neurological evaluation or at the time of starting treatment with Tafamidis free acid 61 mg.

For all patients, the difference between the last follow-up and the start of treatment with Tafamidis (61 or 80 mg) will be checked to ensure it is at least 12 months.

(Last follow-up date - treatment start date* \geq 12 months)

*The first date of treatment with Tafamidis 61 mg or 80 mg

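### The Month 6 to 36 results ignore the recorded stop of tafamidis 61 mg, so change after stopping can enter tables presented as efficacy of 61 mg

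*SAP*

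**What the plan says.** **Who is eligible.** Protocol 9.2 describes patients "with cardiac and neurologic involvement receiving or have received tafamidis free acid 61 mg for at least 12 months". Protocol 9.5 and SAP 4 repeat this, so past users qualify.

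**What is collected.** Protocol 9.3 records treatment status: "Patient is currently on treatment with tafamidis free acid 61 mg (if not, specify stop date". The visit window in the same section is "Routine follow-up visits (up to the last available visit prior to enrollment in the TRAMA study". It is not cut at the stop.

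**Where the stop date is used.** SAP 5 uses it to check 12 months of exposure to 61 mg or, alternatively, 80 mg. For patients still treated, "In such cases where they are on treatment with Tafamidis 61 mg, the date of inclusion in this study will be considered as" the end date. SAP 8.1.1 uses it to describe treatment duration and also tabulates current 61 mg use as yes or no. No other use is stated.

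**How months are assigned.** For NIS, NIS-LL and the scales, SAP 6.1.1 says "All values will be assigned, as of the follow-up date, weighing the assignments based on the recorded follow-ups". A straight line from the start value to the first follow-up fills the scheduled months in between. The one rule that leaves a visit unallocated concerns visits less than 5 months apart, not treatment status. A single follow-up is carried forward (LVCF) to the months that remain. For categorical variables such as PND, SAP 6.1.2 assigns months from a listing of the treatment start date and the follow-up dates. The stop date is not in it.

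**What is reported.** SAP 10 and 12 present Months 6, 12, 18, 24 and 36 for all evaluable patients under objectives worded as efficacy of 61 mg. They set no on-treatment condition and no sensitivity analysis.

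**The concern.** The study has no control group, so within-patient change is its only evidence on efficacy. A value recorded after a patient has stopped describes the drug period and the period after it together. Faster decline after stopping would be charged to 61 mg; slower change would be credited to it.

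The 12-month minimum exposure seems to protect the primary Month 12 result. It does so only if a follow-up visit took place before the stop. Otherwise the Month 12 value is read off a line whose far end lies off treatment. The later months have no such protection.

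**Working it through.** **Inputs from the documents.** Scheduled months 6, 12, 18, 24 and 36, and the assignment rule (SAP 6.1.1). NIS responder limits of <4 at Month 12, <8 at Month 24 and <12 at Month 36 (SAP 12.1, 12.2.1). Minimum exposure of 12 months (Protocol 9.2.1). Expected ATTRv patients: 10 (SAP 4).

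**Not in the documents, so assumed.** Number of stoppers, visit dates and NIS slopes. I also take the start value as measured at treatment start.

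**1. The SAP's own example.** With the first follow-up F months after the start, the assigned change at month m is m × (total change) / F, for scheduled m up to F. F = 25 fills Months 6, 12, 18 and 24. This agrees with the SAP, which allocates up to Month 24.

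**2. Off-treatment share of the line.** For a stop at month S, the share is (F − S)/F.
- S = 12, F = 12: 0%
- S = 12, F = 18: 6/18 = 33%
- S = 12, F = 25: 13/25 = 52%
- S = 12, F = 36: 24/36 = 67%
- S = 24, F = 36: 12/36 = 33%

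**3. Effect on Month 12 when the first follow-up is after the stop.** Let NIS rise by a points per month on treatment and b after. With S = 12, the assigned Month 12 change is 12 × [12a + b(F − 12)]/F. For F = 25:

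| a | b | Change at month 12 under the assumption (12a) | Assigned by SAP 6.1.1 | Class (<4), assumed → assigned |
|---|---|---|---|---|
| 0.2 | 0.2 | 2.40 | 2.40 | responder → responder |
| 0.2 | 0.4 | 2.40 | 3.65 | responder → responder |
| 0.2 | 0.5 | 2.40 | 4.27 | responder → non-responder |
| 0.2 | 0.8 | 2.40 | 6.14 | responder → non-responder |
| 0.4 | 0.2 | 4.80 | 3.55 | non-responder → responder |
| 0.4 | 0.0 | 4.80 | 2.30 | non-responder → responder |

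The third row in full: 12 × (2.4 + 0.5 × 13)/25 = 12 × 8.9/25 = 4.27. The class can move either way or not at all. The 12a column is not observed in such a patient. An on-treatment analysis would make Month 12 missing; it would not recover 2.40.

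**4. Later months when a visit does fall at the stop.** Take visits at months 12 and 36, a stop at month 12, a = 0.2 and b = 0.5. Month 12 stays at 2.4, unaffected. The visits are more than 10 months apart, so the line restarts from month 12. Month 24 = 2.4 + 12 × 0.5 = 8.4 (limit 8) and Month 36 = 2.4 + 24 × 0.5 = 14.4 (limit 12). Both rest on change after the stop.

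**5. LVCF.** A patient whose only follow-up is at month 12, and who then stops, has that value repeated at Months 18, 24 and 36. An on-treatment value then stands in for months off treatment.

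**6. Weight of one patient.** If all 10 ATTRv patients have data, a change of class moves the responder rate by 1/10 = 10 percentage points. If a patient becomes missing, take r responders among 10. Dropping a non-responder raises the rate by r/9 − r/10 = r/90, at most 9/90 = 10 points. Dropping a responder lowers it by (10 − r)/90, also at most 10 points.

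**The case against.** The strongest reply is that keeping every visit is a recognised treatment-policy choice. Cutting at the stop removes patients when they stop; if they stop because they are progressing, that censoring is informative and would flatter 61 mg. This stands, and it is why the all-visits tables should stay. But the SAP does not state such a choice. Protocol 7 says "extra-cardiac clinical data will be collected throughout the follow-up and treatment period with tafamidis 61 mg", which does not settle which visits are analysed.

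A second reply is that Month 12 is normally on drug, since 12 months of treatment are required. This also stands. Month 12 is affected only when a patient stopped and the first follow-up falls after the stop. Moving the class also takes a marked change of slope: at 0.2 then 0.4 points per month with F = 25, the patient stays a responder.

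Third, nothing in the documents shows that anyone stopped or has later visits. That is correct. The yes/no table in SAP 8.1.1 will show how many are no longer on 61 mg, but not which values come from after the stop.

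Two stronger inferences are not supported:
- A reader might take the mention of available therapeutic options in Protocol 9.3 to mean that patients later switched to another ATTR therapy. That remark sits under age at onset and asks why the disease was not treated. It says nothing about switching.
- A reader might want the 12-month follow-up check to count only time on treatment. The protocol criterion counts follow-up after starting treatment, so this would change eligibility and could shrink a very small sample.

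**Conclusion.** The point holds as a conditional one. Followed as written, SAP 6.1.1 and 6.1.2 can put change after stopping into Month 6 to 36 results presented as efficacy of 61 mg. Months 18 to 36 are exposed directly. Months 6 and 12 are exposed only through the straight line from a first follow-up after the stop.

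Size and direction are unknown, because the number of stoppers, their visit dates and their NIS slopes are not given. What can be stated is the off-treatment share of the line (52% for a stop at month 12 and a first follow-up at month 25) and the weight of one ATTRv patient (up to about 10 percentage points of the responder rate, if all 10 have data). It would go too far to say that off-treatment change is being reported as efficacy, or that the primary result is generally contaminated. The change is worth making because the stop date is already collected.

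**What to change.** In SAP 6.1, 10.3 and 12:

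- Flag each follow-up value as before or after the end of the qualifying exposure. Define that end from the exposure SAP 5 accepts (61 mg or 80 mg), so that a move from 80 mg to 61 mg does not count as a stop.
- Show the number of patients on treatment at each month.
- Keep the all-visits tables. Beside them, present an on-treatment analysis of NIS change, responder rates and PND non-progression that uses only visits up to the stop. Do not interpolate from a later visit or apply LVCF past the stop. Leave months without an on-treatment value missing.
- Add the stop date to the SAP 6.1.2 listing.
- Leave inclusion criterion 4 and its check unchanged.

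The cost is SAP wording and a second set of tables. No new data item is needed, because the flag comes from dates already recorded. The on-treatment tables will hold fewer values, and they may be biased by informative censoring if stopping relates to progression. Neither analysis is enough alone, so both should be shown.

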4.1 Inclusion Criteria

Patients must meet all of the following inclusion criteria to be eligible for this study:

1. Be of legal age (>18 years).
2. Have participated in studies B3461028 and/or B3461045 in Spain.
3. Have been treated for at least 12 months with Tafamidis free acid 61 mg.
4. Have a minimum of 12 months of neurological follow-up after starting treatment with Tafamidis free acid 61 mg and have data from previous neurological evaluation or at the time of starting treatment with Tafamidis free acid 61 mg.
5. Have been diagnosed with ATTR amyloidosis polyneuropathy (ATTR-PN), based on any of the following criteria:
 - a. Decreased amplitude in EMG studies, at least two nerves below normal, excluding median, or other nerve entrapment sites.
 - b. A reduction in amplitude by more than 50% by at least two nerves above the patient's baseline value, excluding the median.
 - c. Two different altered fine fiber tests (Sudoscan, CRS, RR interval variability, skin biopsy, etc.).
 - d. A clinical picture consistent with small fiber neuropathy (painful or dysautonomic) and an altered fine fiber test.

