10 VARIABLES AT FOLLOW-UP

Results will be shown at Months **6, 12, 18, 24 and 36 after treatment initiation** (see section 6.1 with re-assignment of visits).

Analyses will be performed on the total population and subgroup based on genotype (ATTRv and ATTRwt). Descriptive analyses will be presented with no comparisons between genotype groups.

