10.3 Neurological variables in patients

10.3.1 NIS (Neuropathy Impairment Score)

See Section 6.1.1 for numerical reassignment of visits.

Descriptive statistics (Mean, SD, Median, Minimum, Maximum, Q1, Q3 and N) of the following quantitative variables will be displayed:

- NIS result (total score ranges from 0 to 244), assigned value for each visit.
- The variable change in NIS between each of the months from start of treatment will be calculated*, which will be the variable corresponding to the increase for each visit in reassignment:
 - Month 6 - start of treatment.
 - Month 12 - start of treatment.
 - Month 18 - start of treatment.
 - Month 24 - start of treatment.
 - Month 36 - start of treatment.
- To the extent possible, paired parametric (t-test) or non-parametric (Wilcoxon) statistical tests will be performed, depending on the sample distribution, to study whether there are differences in the unit change rate for pre- and post-treatment NIS (total and subgroups).

In addition, a listing will be presented per patient for NIS: In the 12 months prior to enrollment in studies B3461028 and/or LTE B3461045 or start of treatment* and follow-up (from month 6 to month 36).

*Note: Start of treatment would refer to the clinical parameters available in the medical history in the 12 months before inclusion in studies B3461028 and/or LTE B3461045, or inclusion in studies B3461028 and/or LTE B3461045 (start of treatment with Tafamidis 61 mg). For each patient, only the most recent value will be collected.

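### SAP 6.1.1 uses one undefined time difference both to scale the rate of change and to place the study months; the two uses agree only if the baseline reading falls on the treatment start date

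*SAP*

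**What the plan says.** SAP 6.1.1, step 1, is headed "Months between visits" and computes a single quantity: "the date difference between the first follow-up and the start time will be calculated for the variable in question". It uses this quantity to decide which visits receive a value: "if the difference is 25 months, visits up to Month 24 will be allocated". Step 2 divides the difference between the follow-up and start-of-treatment values by the same months. Step 3 multiplies the rate, for example "Monthly unit change x 12", and step 4 assigns "Baseline value + Increment for each visit".

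The baseline value need not date from the first day of treatment. Inclusion criterion 4 (SAP 4.1) requires that patients "have data from previous neurological evaluation or at the time of starting treatment with Tafamidis free acid 61 mg". The note in SAP 10.3.1 says: "Start of treatment would refer to the clinical parameters available in the medical history in the 12 months before inclusion in studies", or at inclusion, taking the most recent value. Protocol 9.3 describes the inclusion value itself as coming from the last site visit before inclusion.

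SAP 10 nevertheless reports results at Months 6, 12, 18, "24 and 36 after treatment initiation". SAP 10.3.1 makes the step 3 increment the reported change in NIS. SAP 12.1 refers the primary objective there and adds the Month-12 responder rule of less than 4 points.

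**The concern.** A rate of change needs the time between the two readings. A study month needs the time since treatment began. These are the same number only when the baseline reading was taken on the treatment start date. The SAP allows an earlier reading and provides one number for both purposes, without saying which date it starts from.

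The increment is the primary 12-month NIS change and sets responder status. The same algorithm feeds NIS-LL, Norfolk QoL-DN, FAP-RODS and COMPASS-31. Two programmers could follow 6.1.1 faithfully and report different results for the same patient. SAP 4 expects 10 ATTRv patients, so one patient changing category moves the responder percentage by 1/10, or 10 percentage points.

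**Working it through.** **Notation.** T = months from treatment start to first follow-up. g = months from baseline reading to treatment start. r = true monthly change, assumed constant, as the SAP's own interpolation assumes. Slots are 6, 12, 18, 24 and 36 (SAP 10). The window for g is 0 to 12 months before inclusion (SAP 10.3.1), treating inclusion as the start of treatment, as the SAP does. The values of g and T and the NIS scores below are illustrative; the documents give none.

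**The plan's own example.** A difference of 25 months fills the slots not exceeding 25: Months 6, 12, 18 and 24. This reproduces the SAP.

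**Reading (a): *start time* is the date of the baseline reading.** The difference is g + T.
- Rate = r(g + T)/(g + T) = r, and the Month-12 increment is 12r. Both are correct for a constant slope.
- Step 4 counts from the reading, so slot m lies at treatment month m − g. The Month-12 slot is treatment month 9 at g = 3, month 6 at g = 6, and the day treatment starts at g = 12. At g = 12 the Month-6 slot lies 6 months before treatment.

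**Reading (b): *start time* is treatment start.** The difference is T.
- Rate = r(g + T)/T, so the Month-12 increment is 12r(g + T)/T.
- Two targets are possible: 12 months of progression, 12r, or the change from the old reading to treatment month 12, (g + 12)r.

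| T | g | Increment | Against 12r | Against (g + 12)r |
|---|---|---|---|---|
| 12 | 3 | 15r | 1.25 | 1.00 |
| 12 | 6 | 18r | 1.50 | 1.00 |
| 12 | 12 | 24r | 2.00 | 1.00 |
| 18 | 12 | 20r | 1.67 | 0.83 |
| 24 | 12 | 18r | 1.50 | 0.75 |

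At T = 24 and g = 12 the increment is wrong against both targets.

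**One patient under both readings.** NIS is 20, read 12 months before treatment, and 28 at treatment month 13, so g = 12 and T = 13.
- (a) The difference is 25. The rate is 8/25 = 0.32 and the Month-12 change is 0.32 × 12 = 3.84: responder. The Month-12 level is 20 + 3.84 = 23.84, the estimate for the day treatment starts. Slots are filled to Month 24 (20 + 0.32 × 24 = 27.68, really treatment month 12), although the patient has 13 months on treatment.
- (b) The difference is 13. The Month-12 change is 8/13 × 12 = 7.38: non-responder. The Month-12 level is 27.38.

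**Which target do the cut-offs imply?** The NIS limits in SAP 12.2.1 are 2, 4, 6, 8 and 12 points at Months 6, 12, 18, 24 and 36. The ratios 2/6, 4/12, 6/18, 8/24 and 12/36 all equal 1/3 point per month. That fits a change accrued over m months, which is the 12r target at Month 12.

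**The case against.** The best defence is that the text points to reading (a). Step 1 is headed as time between visits and is computed per variable, step 2 divides a difference between two visit values, and NOTE 3 restarts from the previous follow-up. On that reading the rate and the 12-month increment are right for a constant slope, and the example's 3.84 does not change when the clocks are separated. This stands. It leaves the mislabelled levels and the slots filled past real follow-up, and *start time* is still undefined.

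A reader might infer that the primary change is inflated up to two-fold. The documents do not support that as a general statement. The factor arises only under reading (b), and only against 12 months of progression. SAP 12.1 words the responder change relative to the initial value; against that, the factor at T = 12 is 1.00 and the assigned Month-12 level is the value actually observed. Nor is 2 a bound: step 1 also admits slots close to the difference, so T = 11 with g = 12 gives 23/11 = 2.09, and g could exceed 12 if treatment began after inclusion.

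A reader might also infer that every slot is shifted by g. That holds only for slots filled from the first follow-up. Under NOTE 3, a later follow-up 5 to 10 months after the previous one has its observed value placed in the next open slot.

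Finally, taking the most recent reading shortens g, and g = 12 is the edge of the stated window. That limits the likely size without removing the conflict.

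**Conclusion.** The concern holds in a conditional form. For any patient with g > 0, 6.1.1 either misplaces the study months (reading a) or misscales the increment (reading b, against at least one of the two targets). At g = 0 there is no error. The share of patients with g > 0 is not given, so the effect on the study result cannot be estimated from the documents.

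The direction is not fixed. Reading (b) enlarges worsening and improvement alike when judged against 12 months of progression. Reading (a) reports untreated time under on-treatment labels. The sizes shown rest on a constant slope and on illustrative gaps and scores. The point should be corrected before analysis because it touches the primary variable and the remedy is small.

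**What to change.** In SAP 6.1.1, replace the single difference with two:

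- D = follow-up date minus baseline reading date, the denominator of the rate.
- T = follow-up date minus treatment start date, which decides which slots may be filled.
- g = D − T.

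From the first follow-up, set the Month-m level to baseline + rate × (g + m). State in 10.3.1 and 12.1 that change is measured from the estimated level at treatment start, baseline + rate × g, so that it equals rate × m, in line with the cut-offs. Print that start level so that level and change agree. In the example: start level 20 + 0.32 × 12 = 23.84, Month-12 level 20 + 0.32 × 24 = 27.68, change 3.84, and no slot filled beyond Month 12 from that follow-up.

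Add g to the per-patient NIS listing, and repeat the Month-12 summary in patients with a short gap, for example up to 3 months. This is needed because for g > 0 the rate still mixes untreated and treated time. With assumed progression of 6 points per year before and 3 on treatment, g = T = 12 gives (6 + 3)/24 × 12 = 4.5 against a true on-treatment 3.0.

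The cost is SAP wording, a few lines of code and possibly fewer late slots filled. The sponsor should confirm that the baseline reading date is on the CRF, since the documents do not show this.
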